# 9.0 Removal From Study

9.1 Failure to respond after 2 courses, or only minor response after 4 courses. Discuss with P.I.

9.2 Progressive or relapsed disease

9.3 Patients whose maximum response is only PR, particularly if there is biopsy-proven or metabolically active disease, should be considered strongly for alternative therapy, such as stem cell transplantation. CR/CRu patients who do not attain molecular response after Zevalin and 3-6 months of rituximab should also be considered for alternative therapy options.

9.4 Unacceptable toxicity.

9.5 Patient request.

9.6 Noncompliance with requirements of the protocol (at the discretion of the PI).

# **10.0 Statistical Consideration**

10.1.Primary objective and sample size

The objective of this trial is to determine if R-FND followed by Zevalin and rituximab maintenance therapy, is sufficiently efficacious in the treatment of high-risk follicular lymphoma to merit further study in this disease. Although tumor response can be achieved with standard therapy in the majority of patients, these responses are short-lived. Among 729 high-risk patients treated with standard therapy in a multicenter study (including MDACC), the median time to progression (TTP) was 24 months (8). The new regimen would be regarded as a success if median TTP can be prolonged to 36 months or greater. A maximum of 50 patients will be entered on this single arm trial, at an expected accrual rate of 2 patients per month. The trial will require approximately 25 months for patient accrual and an additional 8 months for patient follow-up. If the trial continues to maximum accrual and sufficient follow-up to observe 30 progression events, then a 95% credible interval for median TTP (assumed to be 36 months) would extend from 27.9 to 52.9 months.

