# **Protocol Body**

# **1.0 Objectives**

1.1 To assess whether the time to progression for these high-risk patients can be prolonged to a median of 36 months, compared to the historical expectation of approximately 24 months.

1.2 To assess the tolerance and efficacy of Y2B8 (Zevalin) after R-FND (rituximab, fludarabine, mitoxantrone, dexamethasone) in patients with high-risk stage III-IV follicular lymphoma

1.3 To assess overall response, failure-free survival, and survival of this strategy compared to our historical experience with FND (fludarabine, mitoxantrone, dexamethasone) alone or R-FND

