7.3 PCR for bcl-2

7.3.1 PCR in the peripheral blood will be followed every 3-4 months during the first 18 months, then every 6 months until month 36, then every 12 months. PCR in the bone marrow will be followed at times of bone marrow sampling, (see Section 7.2.1 and Appendix E), i.e., baseline, before Zevalin, 6-8 weeks after Zevalin, at months 9 and 12, and then every 4-6 months during the first 3 years, and every 12 months subsequently.

7.3.2 For patients who are still PCR positive after Zevalin: proceed to rituximab and explore alternative (off this protocol) treatment options, especially stem cell transplant, which is recommended to be pursued at first evidence of progressive disease by clinical (x-ray, marrow, physical exam) criteria.

7.4 Recommended: Restaging after month 12: every 4 months for 1 year (while on maintenance), then every 4-6 months for 2 years, then yearly (see Appendix E). Beyond year 5, it is recognized that these recommended assessments may not be realistic (due to age, distance, or cost issues). We will nonetheless strive to get this data.

7.5 Optional: Peripheral blood lymphocyte surface markers and Ig's every 3-4 months during therapy, and every 6-12 months off therapy until any abnormalities resolve.

7.6 Marrow cytogenetics: after 4 courses R-FND (before Zevalin): and 12-18 months after Zevalin.

7.7 During Zevalin phase:

- CBC, diff, platelets weekly x 12 wks;
- chemistries monthly x 3 mo;
- urinalysis at 1 and 3 mo;
- immunoglobulins at 3 mo;

• HAMA at times of lab testing/clinic visits post-Zevalin (see Section 7.2), i.e., at about 6-8 weeks after Zevalin, and at months 9 and 12.

7.8 During rituximab maintenance: CBC with differential and SMA every 1-3 months during maintenance

7.9 Outside Physician Participation During Treatment (Some general information regarding outside physician participation can also be found in Appendix G).

7.9.1 MDACC Physician communication with the outside physician is required prior to the patient returning to the local physician. This will be documented in the patient record

7.9.2 A letter to the local physician outlining the patient's participation in a clinical trial will request local physician agreement to supervise the patient's care (Appendix M) and a copy of the chemotherapy instructions will also be sent to the outside physician (Appendix N).

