10.3. Analysis

The distribution of TTP will be estimated by the method of Kaplan and Meier, and accompanied by 95% confidence interval. Summary statistics will be computed for response and toxicity endpoints. All patients who receive any chemotherapy will be included in calculation of these endpoints. Patients lost to follow-up are regarded as failures if response has not been measured, and as censored observations at date of loss for purpose of estimating TTP.

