10.5 At any point in the trial, TTP can be calculated for each patient, with the time interval regarded as censored at the date of last followup if progression has not been observed for a patient. At each interim analysis, we will apply a Bayesian method of updating prior information with TTP data observed to that time. It is assumed that the TTP for each patient is exponentially distributed with median,  $\lambda_{NEW}$ , for the R-FND followed by Zevalin and rituximab maintenance group and  $\lambda_{H}$  for standard treatment. Based on historical data,  $\lambda_{H}$  is assumed to follow an inverse gamma distribution with mean 24 and variance 16.7. To reflect the little prior knowledge of  $\lambda_{NEW}$ , we assume an inverse gamma distribution with the same mean and variance 100. Since the goal of the study is to increase the median TTP by 12 months, the trial will be stopped early if, based on current data, Pr ( $\lambda_{NEW} > \lambda_{H} + 12$  month data) < 0.03. The probability cutoff of 0.03 was chosen to obtain a 0.054 false negative (early stopping) probability if the true median TTP is 36 months.

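### The 25 + 8 months in section 10.1 yields about 16 progressions at the target median, not the 30 behind its only precision figure, and no section says when the final TTP analysis is done

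*Combined protocol and SAP*

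**What the plan says.** Section 10.1 plans at most 50 patients at 2 per month and gives the length of the trial: "The trial will require approximately 25 months for patient accrual and an additional 8 months for patient follow-up". Its next sentence gives the precision for the primary endpoint and opens with a condition: "If the trial continues to maximum accrual and sufficient follow-up to observe 30 progression events". Under that condition the 95% credible interval, for a median assumed to be 36 months, is 27.9 to 52.9 months.

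The success level is in the same section: "The new regimen would be regarded as a success if median TTP can be prolonged to 36 months or greater". Objective 1.1 matches it: "To assess whether the time to progression for these high-risk patients can be prolonged to a median of 36 months". The historical median is 24 months.

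Section 10.3 names the analysis: "The distribution of TTP will be estimated by the method of Kaplan and Meier, and accompanied by 95% confidence interval". It sets no date, minimum follow-up or event count. Section 10.4 describes continuous monitoring, safety reviews and one dated efficacy look, on the first 25 patients, 13 months after the 25th is registered (about month 12.5 + 13 = 25.5). Section 10.5 models TTP as exponential, and for the new regimen's median "we assume an inverse gamma distribution with the same mean and variance 100", the mean being 24.

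Section 7.4 recommends restaging after month 12 "every 4 months for 1 year (while on maintenance), then every 4-6 months for 2 years, then yearly", and adds: "Beyond year 5, it is recognized that these recommended assessments may not be realistic".

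**The concern.** The duration and the precision figure stand next to each other in section 10.1, and a reader will take the second to describe what the first delivers. With a target median of 36 months, 8 months after the last entry looks far too short for 30 of 50 patients to progress.

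Two things are at stake. If the 8 months is followed, the final analysis has about half the events behind the quoted interval, and the planned Kaplan-Meier estimate is cut off below the success level. If it is not followed, the plan gives no other analysis time. In a single-arm trial whose TTP data are reviewed continuously, that leaves the cut-off open to choice after results have been seen.

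**Working it through.** **Inputs.** From section 10.1: N = 50, 2 per month, 8 months of further follow-up, 30 events, medians 36 (target) and 24 (historical). From section 10.5: exponential TTP, and an inverse gamma prior with mean 24 and variance 100. Assumed, because the plan gives no rate: no loss to follow-up, varied below.

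**1. The plan's own figures.** Accrual is 50/2 = 25 months, which agrees.

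For the interval, the prior has shape a = 2 + 24²/100 = 7.76 and scale b = 24 × 6.76 = 162.24. With d events and T person-months the posterior for the median is inverse gamma (a + d, b + ln2 × T). For d = 30 the shape is 37.76, and the ratio of upper to lower 95% limit is 1.90 whatever T is. The plan's ratio is 52.9/27.9 = 1.90, so its interval does rest on about 30 events.

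The exact limits depend on how 36 is taken as the centre:

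| Centring, 30 events | 95% interval |
|---|---|
| posterior mean 36 | 26.1 to 49.6 |
| posterior median 36 | 26.6 to 50.5 |
| posterior mode 36 | 27.5 to 52.3 |
| 1,800 person-months (fitted after the fact) | 27.8 to 52.8 |

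None gives 27.9 to 52.9 exactly. The last is within 0.1 month. Nothing below depends on this.

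**2. Expected progressions.** With even accrual over 25 months, F months of follow-up after last entry and r = ln2/median:

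E = 50 × [1 − (exp(−rF) − exp(−r(25 + F)))/(25r)].

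For median 36, r = 0.01925. At F = 8, E = 50 × [1 − (0.8572 − 0.5297)/0.4814] = 16.0.

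| True median | Expected at month 33 | Simulated 95% range | Pr(≥ 30 by month 33) | F at which E = 30 |
|---|---|---|---|---|
| 24 | 21.7 | 15 to 28 | about 0.01 | 20.0 (month 45.0) |
| 36 | 16.0 | 10 to 22 | below 0.001 | 35.6 (month 60.6) |
| 48 | 12.6 | 7 to 19 | below 0.001 | 51.3 (month 76.3) |

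(Simulation: 20,000 trials per median, one entry each half month.)

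Thirty expected events by month 33 would need a true median of about 14.6 months. Even if all 50 patients had the full 33 months, only 50 × (1 − 2^(−33/36)) = 23.5 would be expected at a median of 36.

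**3. Sensitivity at a median of 36.** Accrual of 1.5 or 2.5 per month gives 18.4 or 14.4 expected events 8 months after last entry. Loss of 2, 5 or 10% per year (assumption) lowers the 16.0 at month 33 to 15.7, 15.3 or 14.6, and moves the expected 30th event to about 38, 44 or 62 months after last entry.

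**4. Kaplan-Meier at month 33.** The longest possible follow-up on planned accrual is 33 months, so an estimated median of 36 or more cannot occur. In simulation the median was reached at all in 32% of trials at a true 36, 78% at 24 and 13% at 48, and was 36 or more in none. At the 30th event, by contrast, the curve is at or below 20/50 = 0.40, so the median is always reached. It was 36 or more in about 45% of trials at a true 36, 89% at 48 and under 2% at 24.

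**5. Precision on a like-for-like basis.** With the section 10.5 prior and posterior median 36, 16 events give 24.6 to 55.5 (ratio 2.25). Thirty events give 26.6 to 50.5 (ratio 1.90).

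**The case against.** The strongest reply is that nothing in section 10.1 is false. The interval is explicitly conditional on enough follow-up for 30 events, the duration is approximate, and the 8 months is never called the analysis date. Restaging under section 7.4 runs for years, so later progressions can be captured. All of this stands. A reader might infer that the two sentences contradict each other, or that the final analysis is fixed at month 33; the documents support neither.

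It is also fair that an unreached Kaplan-Meier median is not a failed trial. Section 10.3 does not say that success is judged on the Kaplan-Meier median, and the section 10.5 model yields an estimate at month 33. Nor do half the events mean half the information: the prior contributes too, and the interval widens from a ratio of 1.90 to 2.25, a moderate loss.

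What the reply does not supply is an analysis time. The 25 + 8 months is the only duration stated. The section 7.4 restaging is a recommendation and is not linked to any TTP analysis. Eight months fits 30 events at neither the historical nor the target median.

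A bare 30-event trigger would have its own gap. Section 10.4 gives a 0.433 chance of early stopping at a true median of 24, with 43 patients on average. That implies about (43 − 0.567 × 50)/0.433 = 34 patients in a stopped trial, of whom about 88% would have to progress. Any trigger therefore needs the full-accrual condition and a fallback.

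**Conclusion.** The point holds as a mismatch between stated duration and stated precision, together with an unspecified time for the final TTP analysis. It should be fixed. At month 33 about 16 progressions are expected if the median is 36 and about 22 if it is 24, against the 30 behind the quoted interval. This rests on full accrual to 50 at 2 per month, exponential TTP and no loss; loss makes it worse, and the accrual rates tried do not rescue it. The statement that Kaplan-Meier cannot show 36 months or more applies only if month 33 is used and accrual runs as planned.

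Three stronger readings are not supported. The interval of 27.9 to 52.9 is not shown to be wrong: its width fits 30 events. The regimen is not barred from success, because the model-based estimate remains available. The early-stopping rule of sections 10.4 and 10.5 is unaffected, since it uses the data to hand at each look and not a final analysis date.

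**What to change.** In section 10.1, replace the statement of 8 further months of follow-up with:

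*If the trial reaches 50 patients, the final TTP analysis will be performed when 30 progressions have been observed, or at a pre-specified latest calendar date if that comes first. Thirty progressions are expected about 36 months after last entry if the median is 36 months and about 20 months after if it is 24, assuming no loss to follow-up, and later with loss. If accrual stops early, the analysis will be performed at a pre-specified follow-up time after last entry.*

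If month 33 is kept instead, state that about 16 progressions are expected then at a median of 36, that the 27.9 to 52.9 interval does not apply at that date, and that a Kaplan-Meier median of 36 months or more cannot be observed. An interval quoted for month 33 should be centred at 36, as in section 10.1: about 24.6 to 55.5, against 26.6 to 50.5 for 30 events on the same basis. Entering the expected data directly (16 events, 830 person-months) gives 21.6 to 48.6, but its posterior median is 31.5, so it should not be set beside the section 10.1 figure.

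Cost: amendment wording, no extra patients, and a later final analysis, by about 28 months at a median of 36 (60.6 − 33) or 12 at 24 (45.0 − 33). The date is uncertain. At a true median of 36 the 30th event falls 20 to 54 months after last entry in 95% of simulated trials (months 45 to 79). The analysis would rely on restaging that section 7.4 only recommends and, for the earliest patients, doubts is realistic beyond year 5, which is why a latest date is needed.

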1.4 To assess the tolerance and efficacy of maintenance therapy with rituximab

1.5 To maximize the 12-month molecular remission rate for patients with high-risk stage III-IV follicular lymphoma

1.6 To correlate the results of quantitative PCR assay with classical PCR and with clinical outcome.

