5.5 Maintenance Rituximab

5.5.1 Candidate patients: All responders (CR/CRu/PR), to start 6-8 weeks after Zevalin. 5.5.2 Schedule:

Rituximab: 375 mg/m^2 IV, a single dose every other month for 12 mo (6 doses total). Start 6-8 weeks after Zevalin, at approximately month 7.

NOTE: Rituximab maintenance can and should start on schedule, even if there is delayed hematologic recovery after Zevalin.

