#### 10.4. Interim monitoring

The trial will be monitored as often as feasible and will be stopped early if, based on current data, it is unlikely that the median TTP following R-FND followed by Zevalin and rituximab maintenance is at least 12 months longer than that achieved with standard therapy (see section 10.5). The probability criterion is recomputed prior to each patient entry (or as often as possible) and requires updating of TTP information for each patient previously entered. This will be accomplished through a web-based computer program and data entry screen provided by the Department of Biostatistics. In the event of insufficient evidence of the superiority of R-FND followed by Zevalin and rituximab maintenance with regard to TTP, the program will print a statement that no further patients should be accrued to the trial.

To obtain operating characteristics of these monitoring procedures, the trial was simulated using several assumed medians for time to progression, with computer generated patients arriving according to a Poisson process at the rate of 2 patients per month. Results follow:

Median TP (months)	Pr (stop early)	# of Patients	Average trial length (months)
12	0.999	23	11.3
24	0.433	43	21.4
36	0.054	49	24.4
48	0.015	50	24.9

In addition to the ongoing monitoring, a planned interim analysis will be performed on the first 25 patients, to be conducted 13 months after registration of patient 25.

Preliminary reviews of safety will also be done: (a) after the enrollment of 10 patients; and (b) after the first 10 patients complete Zevalin therapy.

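### The 8 months of follow-up stated in section 10.1 is shorter than the plan's own 12-month, maintenance and post-Zevalin time points for late entrants, and too short for the 30 events named there

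*Combined protocol and SAP*

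**What the plan says.** Section 10.1 sets the size and pace, "A maximum of 50 patients will be entered on this single arm trial, at an expected accrual rate of 2 patients per month", and then the length: "The trial will require approximately 25 months for patient accrual and an additional 8 months for patient follow-up". It gives no reason for the 8 months. Its next sentence makes the credible interval for median TTP conditional on "sufficient follow-up to observe 30 progression events" and gives no date for that.

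Other sections set per-patient time points:

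- Objective 1.5: "To maximize the 12-month molecular remission rate for patients with high-risk stage III-IV follicular lymphoma".
- Objective 1.4: "To assess the tolerance and efficacy of maintenance therapy with rituximab". Section 5.5.2 starts maintenance at about month 7 and gives "a single dose every other month for 12 mo (6 doses total").
- Section 7.6 schedules marrow cytogenetics "after 4 courses R-FND (before Zevalin): and 12-18 months after Zevalin".
- Section 7.7 places HAMA tests at 6-8 weeks after Zevalin and at months 9 and 12. Section 10.2 lists post-Zevalin toxicity, including HAMA, for tabulation.

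Section 10.4 uses a longer minimum for the first half of the cohort: "a planned interim analysis will be performed on the first 25 patients, to be conducted 13 months after registration of patient 25".

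Sections 7.3.1 and 7.4 continue PCR to month 36 and yearly after that, and restaging for years, with data still sought beyond year 5. Section 10.3 covers patients lost to follow-up. It has no rule for patients who have simply not yet reached a fixed time point.

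**The concern.** A patient entered at month 25 has 8 months of follow-up at month 33. By then that patient has only just reached the point where maintenance begins, and is short of the 12-month molecular assessment and well short of the cytogenetic check. If results are drawn up on the stated timeline, the 12-month rate has an undefined denominator, maintenance tolerance comes partly from unfinished courses, and the only scheduled cytogenetic check after the radiolabelled antibody is absent for a large share of patients. The primary precision statement is affected too, because the stated length and the 30 events sit in the same paragraph and do not fit together at the target median.

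**Working it through.** **Inputs.** 50 patients, 2 per month, 8 months (10.1). Month 12 (1.5). Maintenance from about month 7, six doses two months apart over 12 months (5.5.2). Four 28-day courses for most patients (5.6.3). Zevalin phase 12-16 weeks after the last R-FND course (5.4.3), with the therapeutic dose one week later (5.4.3.1). Cytogenetics 12-18 months after Zevalin (7.6).

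**Assumptions.** Patient i enters at month i/2. Data are cut at month 33. One month is 30.44 days. The last course is counted from its start (week 12) or its end (week 16), since 5.4.3 does not say which.

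**Step 1: the stated figure.** 50/2 = 25 months of accrual, which reproduces; 25 + 8 = 33.

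**Step 2: timing of the later points.** Zevalin falls between week 12 + 12 + 1 = 25 (month 5.75) and week 16 + 16 + 1 = 33 (month 7.59). The sixth maintenance dose is at month 7 + 10 = 17, and the 12-month period ends at month 7 + 12 = 19.

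**Step 3: patients short at month 33.** Patient i is short of time t if i/2 + t > 33. The number short is 2(t - 8), rounded up to a whole patient.

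| Time point | t (months) | Short, of 50 |
|---|---|---|
| Month 12 | 12 | 8 (16%) |
| Sixth maintenance dose | 17 | 18 (36%) |
| End of maintenance | 19 | 22 (44%) |
| 12 months after Zevalin | 17.75-19.59 | 20-24 (40-48%) |
| 18 months after Zevalin | 23.75-25.59 | 32-36 (64-72%) |

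If maintenance is instead dated from the week counts (6-8 weeks after Zevalin), the sixth dose falls at month 17.1-19.4 and 38-46% are short of it.

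**Step 4: the interim.** Patient 25 enters at month 12.5 and the analysis is at 12.5 + 13 = 25.5. None of the 25 is short of month 12.

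**Step 5: progression events.** With exponential TTP (the model in 10.5) and uniform entry, expected events F months after accrual ends are

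E(F) = 50 × {1 - [exp(-λF) - exp(-λ(F + 25))]/(25λ)}, with λ = ln 2/36 = 0.01925.

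For F = 8: 50 × {1 - (0.8572 - 0.5297)/0.4814} = 16.0. For F = 13, 20 and 26 the result is about 19, 23 and 26. Thirty events need F of about 35.6. At a 24-month median, F = 8 gives about 22.

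**Step 6: follow-up needed after the last entry.**

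- Month 12 needs at least 12 months. Using the interim's 13 gives a total of 25 + 13 = 38.
- The latest sixth dose (19.4) and the latest opening of the cytogenetics window (19.6) need about 20, total 45. The 12-month maintenance period ends at month 19 on the section 5.5.2 timing; on the slowest week count it ends at 41 weeks + 12 months = 21.4.
- The close of the cytogenetics window (25.6) needs about 26, total 51. At 20 months, 8-12 of 50 would still be short of it.
- Thirty events at a 36-month median need about 36, total 61.

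**The case against.** The best case against this is that nothing in the documents fixes an analysis, data cut or closure at month 33. The sentence is approximate, and the next one looks to 30 events. Sections 7.3.1 and 7.4 carry PCR and restaging far past month 33. TTP, the primary endpoint, handles short follow-up by censoring (10.3, 10.5). Molecular remission and cytogenetics are not named among the endpoints in 10.2.

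Much of this stands, and it rules out several stronger readings:

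- A reader might infer that late entrants can never reach these time points. The documents do not support that: the assessments are scheduled, so the data arrive late.
- A reader might infer a biased molecular remission rate. If patients not yet at month 12 counted as failures, a true 80% would read as 0.80 × 42/50 = 67%. No section applies that rule; the failure rule in 10.3 covers only patients lost to follow-up. If instead only the unknowns were dropped, about 1.4 of the 8 late entrants would already have progressed at a 36-month median, and 80% would read as 0.80 × 42/43.4 = 77%. The 80% is itself the molecular response rate from an earlier trial (2.3), not a 12-month rate.
- A reader might infer that the interim's 13 months was chosen to secure a 12-month molecular result. Section 10.4 gives no reason. Only the difference, 13 against 8, is a fact.

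What the objection does not remove is the stated duration. It agrees neither with sections 1.4, 1.5, 5.5.2 and 7.6 nor with the 30 events beside it, and no section says what happens at month 33. Section 10.2 does list post-Zevalin toxicity including HAMA, and the month-12 HAMA test is also beyond 8 months.

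**Conclusion.** The point holds as an unreconciled timeline, not as a loss of data. If the analysis or closure takes place at month 33 with even accrual of 2 per month, the shortfalls run from 16% at month 12 to 64-72% at 18 months after Zevalin, and about 16 events are expected at the target median instead of 30. The shares are of all 50 enrolled. Evaluable counts would be smaller, because molecular remission applies only to patients PCR-positive at baseline (8.2), and maintenance and post-Zevalin cytogenetics only to those who get that far. The ranges reflect the Zevalin timing in 5.4.3 and, for maintenance, the choice between the sixth dose and the end of the period. The event counts rest on the exponential model.

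**What to change.** In section 10.1, replace the 8 months with the minimum follow-up after the last entry before each endpoint is reported, and restate the total duration:

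- 12-month molecular remission: at least 13 months (total about 38).
- Maintenance tolerance: about 20 months (about 45).
- Marrow cytogenetics, if the full 12-18 month window is to be covered: about 26 months (about 51).
- TTP with the stated precision: about 36 months, or when 30 progressions have occurred (about 61).

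In section 10.3, state that the 12-month molecular remission rate is reported among patients PCR-positive at baseline, and only once each has reached month 12, progressed, died or been lost. Because section 8.2 requires two negative blood tests at least 2 months apart, also say whether the confirming test must fall by month 12; if it may fall later, the minimum becomes about 14 months.

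The change is to wording only. Sections 7.3.1, 7.4 and 7.6 already schedule the assessments, so no patients, visits or tests are added. The cost is later reporting: about 5, 12, 18 and 28 months beyond the stated month 33.

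### The 95% credible interval of 27.9 to 52.9 months in section 10.1 does not follow from 30 events, a median of 36 months and the prior in section 10.5

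*Combined protocol and SAP*

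**What the plan says.** Section 10.1 gives the expected precision of the completed trial. The sample size is capped ("A maximum of 50 patients will be entered on this single arm trial") and, conditional on "sufficient follow-up to observe 30 progression events", the text states: "then a 95% credible interval for median TTP (assumed to be 36 months) would extend from 27.9 to 52.9 months". No prior, total follow-up time or type of interval is given beside these limits.

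The plan's only Bayesian model is in section 10.5. On the distribution of time to progression (TTP) it says: "It is assumed that the TTP for each patient is exponentially distributed with median". For the new regimen's median it says: "we assume an inverse gamma distribution with the same mean and variance 100", where the shared mean is 24 months. Section 10.4 describes its operating characteristics in similar terms ("the trial was simulated using several assumed medians for time to progression"); there an assumed median is the true value used to generate data.

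**The concern.** For exponential data with an inverse gamma prior on the median, the interval is a fixed calculation once the prior, the number of events and the follow-up time are known. A figure printed to 0.1 month should therefore be recoverable. This one is not, under any meaning of 36 that was tried.

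The sentence stands in the sample-size section and is the plan's statement of how well the full trial would estimate its primary endpoint. A reader will compare the lower limit with the historical 24 months. As printed, the margin is 27.9 − 24 = 3.9 months. Under the readings that use the 10.5 prior it is 0.5 to 3.5 months. The printed interval therefore gives a more favourable picture than the stated inputs support.

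**Working it through.** **Inputs.** Events d = 30 and median 36 (10.1); exponential TTP with median λ (10.5); prior for λ inverse gamma (IG) with mean 24 and variance 100 (10.5).

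**Prior.** Shape = 24²/100 + 2 = 7.76. Scale = 24 × (7.76 − 1) = 162.24.

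**Posterior.** With total follow-up T patient-months, λ given the data is IG with shape 7.76 + 30 = 37.76 and scale S = 162.24 + ln2 × T. The equal-tailed 95% limits are S/50.721 and S/26.689, where the divisors are the 97.5% and 2.5% quantiles of a gamma(37.76) variable.

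**Attempt to reproduce the printed figure: the ratio.** The ratio of the limits depends only on the shape: 50.721/26.689 = 1.900. The printed ratio is 52.9/27.9 = 1.896, or 1.891 to 1.901 allowing for rounding. So the printed spread agrees with the 10.5 prior plus 30 events.

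**Attempt to reproduce the printed figure: the location.** Each meaning of 36 fixes S:

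| What equals 36 | S | 95% limits (months) |
|---|---|---|
| Observed median (ln2 × T = 30 × 36 = 1,080; T = 1,558) | 162.24 + 1,080 = 1,242.24 | 24.5 to 46.5 |
| Posterior mean | 36 × 36.76 = 1,323.36 | 26.1 to 49.6 |
| Posterior median | 36 × 37.427 = 1,347.38 | 26.6 to 50.5 |
| Posterior mode | 36 × 38.76 = 1,395.36 | 27.5 to 52.3 |
| **Printed in 10.1** | | **27.9 to 52.9** |

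Taking 36 as the true median, the sense used in 10.4, 40,000 simulated trials (50 patients, Poisson accrual of 2 per month, analysed at the 30th progression) gave average limits of 24.5 to 46.6, with mean follow-up of about 1,560 patient-months.

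**Solving backwards.** With shape 37.76, a lower limit that rounds to 27.9 needs S between 1,412.6 and 1,417.7. An upper limit that rounds to 52.9 needs S between 1,410.5 and 1,413.2. Both hold only for S = 1,412.6 to 1,413.2. At S of about 1,413:

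- observed median = (1,413 − 162.24)/30 = 41.7 months, from about 1,804 patient-months, against 1,558 for an observed median of 36;
- posterior mean 38.4, posterior median 37.8, posterior mode 36.5.

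None of these is 36.

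**Other priors, observed median 36.** Density proportional to 1/λ: shape 30, scale 1,080, limits 25.9 to 53.4. Prior recentred at mean 36 with variance 100, IG(14.96, 502.56): 26.8 to 48.3. The historical prior (mean 24, variance 16.7): 23.2 to 37.5. Log-normal: 25.2 to 51.5. None matches.

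**Position relative to 24 months.** Under the four readings in the table, the posterior probability that the median exceeds 24 months is 0.982, 0.994, 0.996 and 0.998.

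**The case against.** **The figure is nearly recoverable.** If 36 is entered as the average follow-up per patient, T = 50 × 36 = 1,800, S = 162.24 + 0.6931 × 1,800 = 1,409.9, and the limits are 27.8 to 52.8, within 0.1 month of those printed. This may be how the number arose, but the plan does not say so. It also does not rescue the sentence: 30 events in 1,800 patient-months is an observed median of 0.6931 × 1,800/30 = 41.6 months.

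**The posterior-mode reading is close.** It misses by 0.4 and 0.6 months, about 1.4% and 1.2%. Nothing in the plan says that 36 is a posterior mode, and a deterministic figure quoted to 0.1 month should match.

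**Section 10.1 does not specify an equal-tailed interval.** With the mode at 36, a highest-density interval computed on the rate scale and inverted gives 27.9 to 53.5. The lower limit then matches, but the upper does not. What stands is that the statement that both printed limits are too high applies to equal-tailed intervals.

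**The sentence assumes the trial was not stopped early.** Conditioning a simulation on passing the 10.5 rule raised the average limits only to about 25.0 to 47.6. That is indicative only, because the rule as coded stopped about 20% of trials at a true median of 36, against the plan's 0.054.

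**The prior is inferred, and the sentence is illustrative.** Both are true. Section 10.5 introduces its prior for interim analyses, and the planned final analysis in 10.3 is Kaplan-Meier with a confidence interval. The matching ratio makes use of the 10.5 prior likely, but not certain. The size of the error therefore cannot be pinned to one value.

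**Conclusion.** The concern holds. The printed interval does not follow from 30 events, a median of 36 months and the 10.5 prior, and none of the alternative priors or interval types tried gives both limits. Against the equal-tailed intervals under the 10.5 prior, the lower limit is too high by 0.4 to 3.4 months and the upper by 0.6 to 6.4 months, depending on what 36 denotes. The largest gap is for an observed median of 36 months.

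The error is in location. The ratio of the limits is right; in absolute terms the printed interval is wider (25.0 months) than the one for an observed median of 36 (22.0 months).

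The consequence is limited. The stopping rule in 10.5, the operating characteristics in 10.4 and the analysis in 10.3 do not use this interval, and 24 months lies outside the equal-tailed interval in every reading under the 10.5 prior. The point should be corrected because it misstates the precision expected for the primary endpoint. The result rests on the exponential model and the 10.5 prior, the only ones the plan gives for this median.

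**What to change.** Recompute the interval in 10.1 and state beside it the prior, the 30 events, the total follow-up time, the interval type and which quantity is set to 36.

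- Observed median under the 10.5 prior: print 24.5 to 46.5 months, with 1,558 patient-months.
- Posterior mean, median or mode: name it and print 26.1 to 49.6, 26.6 to 50.5 or 27.5 to 52.3 respectively.
- Average follow-up of 36 months per patient: say that this is what was entered, and do not describe it as a median TTP of 36 months.
- A different prior: give its parameters and the interval that follows from them.

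The cost is one sentence. Under the 10.5 prior with equal-tailed limits, both limits move down, so the lower limit becomes less favourable. Sample size, stopping rule, analysis and patient procedures do not change.
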